3.0 SCHEDULE OF STUDY PROCEDURES

		Periods 1 and 2 (a)							Early				
	Screening	Pretreat- ment Day Treatment Day (c)		Safety Follow-Up (b)	Termina- tion Visit								
Study Day	Days -30 to -3	-2	-1	1	2	3	4	5	6	7	8	Post- Treatment 2 Day 20±2	
Administrative Procedu										,		Day 2012	
Confinement		X	X						T T	X			
Informed consent	X	21	71							21			
Inclusion/exclusion criteria (d)	X	X	X	X									
Demographics/ medical history	X												
Medication history	X												
Concurrent medical	X												
conditions													
Clinical Procedures/Asso	essments												
Full physical examination	X	X								X			X
Psychiatric examination	X												
Height	X												
Weight, and BMI	X												
Vital signs (oral [floor of the mouth]/ tympanic temperature) (e)	X	X	X	X						X	X	X	X
Concomitant	X	X	X	X						X	X	X	X
medications (e)													
ECG	X	X								X			X
C-SSRS	X	X								X		X	X
CDSS	X												
SAS	X												
AIMS PANSS	X	X								X			
EBC test (f)	Λ	Λ	X							Λ	X (f)		
ERPs (f, g)			X								X (f)		
Resting state EEG (f)			X								X (f)		
BACS cognitive battery (f)		X	Λ							X (f)	A (1)		
Dispense study medication (h)				X									
Study drug dosing (c) (h)				X	X	X	X	X	X	X	X		
AE assessment (e)	X	X	X	X				 	T	X	X	X	X
Laboratory Procedures												-	
Clinical laboratory tests (hematology, serum chemistry, urinalysis) (i)	X	X									X		X
Hepatitis panel (HBsAg and Anti-HCV)	X												
FSH	X												
Pregnancy test (hCG) (i) (j)	X	X								X		X	X
Drug screen (i)	X	X								X			X

			Periods 1 and 2 (a)								Early		
		Pret	reat-					Safety	Termina-				
	Screening	men	t Day			T	reatm	ent D	ay (c)			Follow-Up (b)	tion Visit
												Post-	
	Days											Treatment 2	
Study Day	-30 to -3	-2	-1	1	2	3	4	5	6	7	8	Day 20±2	
PK Evaluations													
PK blood collection (m)				X						X	X		X
PD/Biomarker Evaluation	ons												
Blood collection (D- and				X						X	X		X
L-serine) (n)													

AE=adverse event, BMI-body mass index, ERP=event-related field, FSH=follicle-stimulating hormone, HBcAg=hepatitis B core antigen, hCG=human chorionic gonadotropin, HCV=hepatitis C virus, PANSS=Positive and Negative Syndrome Scale.

- (a) A washout interval of 14 to 21 days will separate the last dose of study drug in Period 1 and the first dose in Period 2.
- (b) A follow-up safety visit will be conducted 10 to 14 Days post-treatment Period 2.

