- (c) Assessments on Days 7 and 8 may be performed 1 day before or after (ie, Day 6 or 8 for Day 7 and Day 7 or 9 for Day 8). If the Day 8 assessments are conducted on Day 9, study drug dosing duration will be extended for 1 additional day as well.
- (d) Inclusion/exclusion criteria will be assessed only in Period 1.
- (e) Vital signs, concomitant medications and AE assessment on Days 2 to 6 to be performed only on subjects who attend the clinic site for any reason. Vital signs will be conducted for safety only and will not be entered into the database for these visits.
- (f) Day 8 EBC, ERP, and EEG assessments are to be performed at approximately (\pm 1 hour) the same time as on Day -1, and the Day 7 BACS cognitive battery assessments are to be performed at approximately (\pm 1 hour) the same time of day as on Day -2.
- (g) Procedures to be conducted only in subjects who receive at least 1 dose of study medication and are assessed within 36 hours of the last dose.
- (h) Study drug intake on Days 2 to 6 may be supervised by a caregiver or family member, conducted at the investigator site or supervised by a qualified designee.
- (i) These tests can be repeated at any time at investigator discretion.
- (j) Serum Beta hCG at Screening and at the Final Visit, at other visits urine Beta hCG determination on women of childbearing potential only.

(m) Blood samples (approximately 4 mL) will be collected from each subject for the determination of plasma concentrations of TAK-831 at the following time points: Day 1 (predose and at 0.25 to 2 hours and 3 to 6 hours postdose), Day 7 (predose and at 0.25 to 2 hours and 3 to 6 hours postdose), and Day 8 (predose). One additional blood sample will be collected for subjects at the Early Termination Visit, if applicable. The sampling schedule may change based on emerging data but will not exceed the number of planned samples.

(n) Blood sample (6 mL) will be collected for analysis of plasma concentrations of D- and L-serine immediately following PK blood collections on Day 1 (predose and 3 to 6 hours postdose), Day 7 (predose and 3 to 6 hours postdose), and Day 8 (predose). Time of sample collection, time since last dose administered and time of last meal should be recorded for each sample collection. Samples may be analyzed for other amino acids, but total blood volume collected will not change.

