7.1 Inclusion Criteria

In order to be eligible for participation in this study, the subject or caregiver must:

- 1. Understand the study procedures and agree to participate by providing written informed consent.
- 2. Be willing and able to comply with all study procedures and restrictions (see Sections 7.3 and 7.4 for a summary of restrictions).
- 3. Be male or a female aged 18 to 60 years, inclusive, at the Screening Visit.
- 4. Have a body BMI \geq 18.5 and \leq 40.0 (kg/m²) at the Screening Visit.
- 5. Be judged to be in good health by the investigator, based on clinical evaluations including laboratory safety tests, medical history, physical examination, 12-lead ECG, and vital sign measurements performed at the Screening Visit and prior to administration of the initial dose of study drug/invasive procedure.
- 6. Meet the following birth control requirements:
 - Is a male subject who is sterile or agrees to use a barrier method of contraception (eg, condom with or without spermicide) from study drug administration on the first day of the first dose until 95 days after the last dose of study drug administration. No restrictions are required for a vasectomized male subject provided the subject is at least 1 year post-bilateral vasectomy procedure prior to study drug administration on first day of the first dose. A male subject whose vasectomy procedure was performed less than 4 months prior to study drug administration on the first day of the first dose must follow the same restrictions as a nonvasectomized male. Appropriate documentation of surgical procedure should be provided.
 - Is a male subject who agrees to not donate sperm from study drug administration on the first day of the first dose until 95 days after the last dose of study drug administration.
 - Is a female subject with no childbearing potential, defined by at least 1 of the following criteria:
 - a) Postmenopausal (defined as 12 months of spontaneous amenorrhea in females aged >45 years, 6 months of spontaneous amenorrhea in females aged >45 years with serum FSH levels >40 mIU/mL). Appropriate documentation of FSH levels is required.
 - b) Surgically sterile by hysterectomy and/or bilateral oophorectomy with appropriate documentation of surgical procedure.
 - c) Had a tubal ligation with appropriate documentation of surgical procedure.
 - d) Has a congenital condition resulting in no uterus.

- Is a female subject with child-bearing potential must have the following criteria:

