Appendix D Pregnancy and Contraception Contraception and Pregnancy Avoidance Procedure

Male Subjects and Their Female Partners

From signing of informed consent, throughout the duration of the study, and for 95 days after last dose of study drug, nonsterilized** male subjects who are sexually active with a female partner of childbearing potential* must use barrier contraception (eg, condom with or without spermicidal cream or jelly). In addition, they must be advised not to donate sperm during this period. Females of childbearing potential who are partners of male subjects are also advised to use additional contraception as shown in the list containing highly effective/effective contraception below.

Female Subjects and Their Male Partners

From signing of informed consent, throughout the duration of the study, and for 35 days after last dose of study drug, female subjects of childbearing potential* who are sexually active with a nonsterilized male partner** must use a highly effective/effective method of contraception (from the list below).

For studies in which teratogenicity/genotoxicity/embryotoxicity has been demonstrated (investigational medicinal product or comparator or background medication), or there is a lack of adequate reproductive toxicity data, female subjects should be instructed to use two highly effective methods of contraception/one highly effective and one effective method (from the list below).

In addition they must be advised not to donate ova during this period.

Definitions and Procedures for Contraception and Pregnancy Avoidance

The following definitions apply for contraception and pregnancy avoidance procedures.

- * A woman is considered a woman of childbearing potential, ie, fertile, following menarche and until becoming post-menopausal unless permanently sterile. Permanent sterilization methods include hysterectomy, and bilateral oophorectomy. A postmenopausal state is defined as no menses for 12 months without an alternative medical cause. A FSH level in the postmenopausal range (FSH >40 IU/L) may be used to confirm a post-menopausal state in younger women (eg, those <45 year old) or women who are not using hormonal contraception or hormonal replacement therapy. However, in the absence of 12 months of amenorrhea, a single FSH measurement is insufficient.

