 - c) Assessment of subject compliance through questions such as
 - i. Have you used the contraception consistently and correctly since the last visit?

- ii. Have you forgotten to use contraception since the last visit?
- iii. Are your menses late (even in women with irregular or infrequent menstrual cycles a pregnancy test must be performed if the answer is "yes")
- iv. Is there a chance you could be pregnant?
- 6. In addition to a negative serum hCG pregnancy test at Screening, female subjects of childbearing potential must also have confirmed menses in the month before first dosing (no delayed menses), a negative serum hCG pregnancy test at predose on Day 1 prior to receiving any dose of study medication. In addition, subjects must also have a negative serum/urine hCG pregnancy test at any time during the study, if requested by the clinical site.

General Guidance With Respect to the Avoidance of Pregnancy

Such guidance should include a reminder of the following:

- contraceptive requirements of the study.
- reasons for use of barrier methods (ie, condom) in males with pregnant partners.
- assessment of subject compliance through questions such as:
 - Have you used the contraception consistently and correctly since the last visit?
 - Have you forgotten to use contraception since the last visit?
 - Are your menses late (even in women with irregular or infrequent menstrual cycles a pregnancy test must be performed if the answer is "yes")
 - Is there a chance you could be pregnant?

Pregnancy

Women of childbearing potential will be included in this study.

If any subject is found to be pregnant during the study she should be withdrawn and any sponsor-supplied drug and should be immediately discontinued. In addition, any pregnancies in the partner of a male subject during the study or for 95 days after the last dose should also be recorded following authorization from the subject's partner.

Should the pregnancy occur during or after administration of blinded drug, the investigator must inform the subject of their right to receive treatment information. If the subject chooses to receive unblinded treatment information, the individual blind should be broken by the investigator. Subjects randomized to placebo need not be followed.

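### Section 7.1 and Appendix D classify some women oppositely for childbearing potential, and no text says which definition governs contraception and on-study pregnancy testing

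*Protocol*

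**What the plan says.** **Section 7.1, inclusion 6.** A woman over 45 has no childbearing potential after 12 months of spontaneous amenorrhoea, or by a second route: "6 months of spontaneous amenorrhea in females aged >45 years with serum FSH levels >40 mIU/mL". Documented tubal ligation also qualifies (item c). The requirement for a highly effective contraceptive method applies to women with childbearing potential.

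**Appendix D.** "A postmenopausal state is defined as no menses for 12 months without an alternative medical cause". This rule has no age limit. FSH above 40 IU/L may help confirm menopause in younger women, but "in the absence of 12 months of amenorrhea, a single FSH measurement is insufficient". Hysterectomy and bilateral oophorectomy are the permanent sterilisation methods named; bilateral tubal occlusion appears instead in the list of contraceptive methods. Item 6 requires a woman of childbearing potential to have had menses confirmed in the month before first dosing, and "a negative serum hCG pregnancy test at predose on Day 1 prior to receiving any dose of study medication". Item 5 describes the regular on-study tests as serum tests.

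**Section 3.0, schedule.** FSH is marked once, at Screening. Pregnancy tests are marked at Screening, Day -2, Day 7, Follow-Up and Early Termination. Note (j) sets the specimen: "Serum Beta hCG at Screening and at the Final Visit, at other visits urine Beta hCG determination on women of childbearing potential only". Note (i) adds: "These tests can be repeated at any time at investigator discretion".

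**Section 9.1.2** assesses eligibility against Section 7.0. Section 7.1 points to Appendix D only for what counts as highly effective contraception.

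**The concern.** The childbearing-potential label decides who must use contraception and who has the on-study urine tests. With two definitions in force, a site can follow Section 7.1 correctly and dose a woman whom Appendix D regards as fertile, without either precaution. The same woman could not meet Appendix D's confirmed-menses rule, so one part of the protocol admits her and another would bar her from dosing. Section 4.4 states that subjects gain no benefit from this study, which makes clear pregnancy rules worth having.

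Amendment 06 widened the group. Raising the upper age from 50 to 60 extends the over-45 range from 46-50 to 46-60.

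The Day 1 serum test is a lesser matter. Appendix D makes it mandatory but the schedule does not contain it, so a site that follows the schedule exactly deviates from Appendix D.

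**Working it through.** The plan gives no figure to reproduce. The check sets the two definitions side by side and then counts schedule marks.

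**Units.** 40 mIU/mL equals 40 IU/L, so the FSH thresholds are the same and do not explain the difference.

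**Classification.** The menopause rows assume a woman who is not surgically sterile.

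| Woman | Section 7.1 | Appendix D | Same? |
|---|---|---|---|
| Over 45, 12 months or more | No childbearing potential | Postmenopausal | Yes |
| Over 45, 6 to under 12 months, one FSH >40 | No childbearing potential | Fertile | **No** |
| Over 45, 6 to under 12 months, FSH not >40 | Childbearing potential | Fertile | Yes |
| Over 45, under 6 months | Childbearing potential | Fertile | Yes |
| 45 or under, 12 months or more, no other cause | Childbearing potential | Postmenopausal | **No** |
| Tubal ligation | No childbearing potential | Not named as permanent sterilisation; tubal occlusion is a contraceptive method | **No** |

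The second row is the one that matters for safety. Its width is 12 − 6 = 6 months of amenorrhoea. With one scheduled FSH, the woman has only the single measurement that Appendix D calls insufficient.

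**Tests at stake.** Urine tests fall on Day -2 and Day 7 in each of 2 periods: 2 × 2 = 4. This takes the Follow-Up or Early Termination visit as note (j)'s Final Visit. The figure is an upper limit. It applies only if the site reads note (j) with Section 7.1's definition, and note (j) does not say which to use.

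**Day 1 test.** The pregnancy-test row has 5 marks, 0 of them on Day 1. The last scheduled test before dosing is the Day -2 urine test. There is no Day 0 (SAP Section 7.1.2), so Day -2 to Day 1 is 2 days. Those days fall within the 2-night stay described in Sections 6.1 and 9.3.4.

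**Number affected.** The documents do not give it. The range runs from 0 to the number of women among up to 32 subjects.

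**The case against.** The strongest reply is that the protection may not be lost at all. Appendix D says its definitions apply to contraception and pregnancy-avoidance procedures. On that reading Section 7.1 settles entry only, and the woman in the 6-month band is still tested and still uses contraception. This stands as a possible reading, and it makes the loss conditional. It does not remove the conflict: no text ties note (j) to either definition, and on this reading the confirmed-menses rule would bar a woman whom Section 7.1 admits.

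Other safeguards also count. Section 9.2.15.2 lists serum beta-hCG for females generally. Exclusion 7 bars any woman with a positive pregnancy test. Note (j)'s restriction can be read as covering only the urine tests, and note (i) permits repeats. These reduce the risk at entry, but they neither require contraception nor schedule tests during treatment.

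On the Day 1 test, inclusion 6 asks only for negative tests at Screening and Baseline, which the schedule provides. With a Day -2 test and confinement until dosing, the residual risk is small. What stands is the mismatch in wording.

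A reader might go further and treat two other drafting points as eligibility faults. Appendix D accepts true abstinence in item 1 and rejects abstinence without qualification in item 3. The Study Summary asks for 2 forms of contraception, while Section 7.1 asks for one highly effective method. The documents do not support that weight. Item 1 defines what it accepts. Appendix D's paragraph on female subjects and consent element 25 in Appendix B limit the contraception duty to sexually active women. Appendix D also makes two methods conditional on the reproductive toxicity findings or on a lack of adequate data. Both points are tidying.

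**Conclusion.** The conflict is real and low in severity. For women over 45 with 6 to under 12 months' amenorrhoea and one FSH above 40, Section 7.1 and Appendix D give opposite answers, and nothing says which prevails. The consequence, no required contraception and up to 4 urine tests not done, rests on one assumption: that the site carries Section 7.1's classification into note (j).

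A reader might infer that women will be dosed unprotected. The documents show only that the wording allows it. The number of women concerned may be 0, and the Screening serum test and exclusion 7 may still apply to them.

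It is also tempting to conclude that Appendix D is simply the safer text and should be copied into Section 7.1. That does not follow. Appendix D has no age limit, so copying it would release women aged 45 or under with 12 months' amenorrhoea from contraception and urine testing that Section 7.1 now requires.

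The Day 1 serum test is a secondary wording mismatch with little practical risk. None of this affects the primary analysis.

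**What to change.** At the next amendment:

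1. Delete the 6-month-plus-FSH route from Section 7.1. Keep the 12-month rule with its limit to women over 45.
2. Make Appendix D's definition match, including the age limit and the status of tubal ligation.
3. State that this single definition governs eligibility, contraception and note (j) testing.
4. Say whether the confirmed-menses rule in Appendix D item 6 is meant to exclude women of childbearing potential with prolonged amenorrhoea: those over 45 with 6 to under 12 months, and those aged 45 or under with 12 months or more. Under the single definition neither group could meet it.
5. Amend Appendix D items 5 and 6 to accept the Day -2 test and the specimen types in note (j).

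The cost is protocol wording and a matching check of the consent form. A few women (number unknown, possibly 0) move into contraception and testing, or out of the study if the menses rule is kept for them. Item 5 adds no test. If the sponsor prefers to keep the Day 1 serum test, it must be added to the schedule, with a statement of whether it applies in both periods. It could share the Day 1 predose PK blood draw in note (m), but the result would be needed before dosing and could delay the first dose.

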Appendix E Detailed Description of Amendments to Text

The primary sections of the protocol affected by the changes in Amendment No. 06 are indicated. The corresponding text has been revised throughout the protocol.

Change 1: Updated entry criteria.

The primary changes occur in Section 7.0 SELECTION AND DISCONTINUATION/WITHDRAWAL OF SUBJECTS

Initial wording:

7.1 Inclusion Criteria

3. Be male or a female aged 18 to 50 years, inclusive, at the Screening Visit.

Amended 7.1 Inclusion Criteria

or new

wording:

3. Be male or a female aged 18 to 60 years, inclusive, at the Screening Visit.

....

Rationale for change: Inclusion criterion 03 revised to increase the maximum subject age from 50 to 60 years, which will allow for increasing patient recruitment.

The following sections also contain this change:

- Section 1.0 STUDY SUMMARY
- Section 6.1 Study Design and Description

A Phase 2 Randomized, Double-Blind, Placebo-Controlled, Cross-Over Study to Evaluate Pharmacodynamic Effects, Safety, Tolerability, and Pharmacokinetics of Multiple Oral Doses of TAK-831 in Adult Subjects With Schizophrenia

ELECTRONIC SIGNATURES

Signed by	Meaning of Signature	Server Date (dd-MMM-yyyy HH:mm 'UTC')

#### 3.0 LIST OF ABBREVIATIONS

AE adverse event

AIMS Abnormal Involuntary Movement Scale

ALT alanine aminotransferase
ASL arterial spin labeling
AST aspartate aminotransferase
ASSR auditory steady state response

ANOVA analysis of variance
ANCOVA Analysis of covariance

BACS Brief Assessment of Cognition in Schizophrenia

CDSS Calgary Depression Scale Score

C-SSRS Columbia Suicide Severity Rating Scale

Cz midline central electrode DNA deoxyribonucleic acid

DSM-5 Diagnostic and Statistical Manual of Mental Disorders, Fifth Edition

EBC eyeblink conditioning ECG Electrocardiogram

eCRF electronic case report form
EEG electroencephalography
ERP event related potential
Fz midline frontal electrode
MAV markedly abnormal value

MedDRA Medical Dictionary for Regulatory Activities

MID monetary incentive delay

MMRM mixed model for repeated measurements

MMN mismatch negativity

MRI magnetic resonance imaging

PD Pharmacodynamics
PK Pharmacokinetic
PT preferred term

Pz midline parietal electrode

QTcF QT interval with Frederica correction method

RNA ribonucleic acid
SAE serious adverse event
SAS Simpson Angus Scale
SOC system organ class

TEAE treatment-emergent adverse event

ULN upper limit of normal WBC white blood cell

[figure not shown]
#### 4.0 OBJECTIVES

# 4.1 Primary Objective

 To determine whether TAK-831 is superior to placebo in improving cerebellar function as measured with the average % of conditioned responses during the eyeblink conditioning (EBC) test.

# 4.2 Secondary Objectives

- To determine whether add-on TAK-831 compared to placebo improves sensory processing as measured by event related potentials (ERPs) mismatch negativity (MMN) and p300.
- To determine whether add-on TAK-831 compared to placebo improves the auditory steady-state response (ASSR) to 40 Hz stimulation.
- To determine whether add-on TAK-831 compared to placebo improves the composite score
  of the BACS battery.
- To assess the safety and tolerability of TAK-831.
- To assess the pharmacokinetics (PK) of TAK-831.
- To assess the pharmacodynamics (PD) of TAK-831 by measurement of plasma D-serine and L-serine levels, as well as plasma D-serine: total serine ratios.

